6.6 Restrictions

6.6.1 Smoking Restrictions and Restrictions to the Smoking Abstinence Arm

To avoid cross contamination between the 3 study arms, subjects must use THS 2.2 and CC must in separate rooms and subjects allocated to the SA arm should not have access to the smoking rooms. All precautions should be taken to remove any temptation to smoke for subjects who are randomized to the SA study arm.

In the THS 2.2 and SA arms, subjects will not be allowed to smoke any CC or use any nicotine/tobacco containing products (including NRT) from Day 1 (06:30 AM) until Day 5 (11:00 PM). In the CC arm, subjects will not be allowed to use the THS 2.2, any nicotine/tobacco containing products and other CC than collected to the site by the subject.

During the confinement period, smoking will generally only be allowed during the designated smoking times, from 06:30 AM to 11:00 PM. Smokers will not have free access to their CC or THS 2.2; these will be dispensed by the study site collaborator individually as described in Section 6.5.1.

Smoking will not be allowed during assessments on the Admission Day at the discretion of the site. Smoking is also not allowed from Day 5, 11:00 PM until the spirometry has been performed on Day 6.

In general, the performance of scheduled procedures has priority over the wish of a subject to smoke. However, this is different at Day 5 due to the assessment of the nicotine profile. If the subject wants to smoke at Day 5 around the time of the blood draw, he/she should inhale/smoke first and the blood will be drawn after the tobacco stick/cigarette has been inhaled/smoked.

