- CC Arm: 40 subjects, *ad libitum* use of their preferred CC brand.
- SA Arm: 40 subjects who will abstain from smoking.

Subjects will be informed of their randomized study arm by the study site collaborator on Day 1 prior to 06:30 AM.

- Exposure period (from Day 1, 06:30 AM until Day 5, 11:00 PM):

The exposure period will consist of 5 days of *ad libitum* use of the assigned product between 06:30 AM and 11:00 PM in THS 2.2 and CC arms. Use of any tobacco/nicotine containing product other than the assigned product will not be allowed and may, at the discretion of the Investigator, result in the subject withdrawal from the study.

Subjects in the SA arm will be asked to abstain from smoking any nicotine/tobacco containing product and will not be provided with medication to support SA.

The end of the 24-h urine collection period for Day 5 will end in the morning on Day 6 prior to Discharge.

- Day of Discharge (Day 6) (from Day 5, 11:01 PM to time of Discharge):

Procedures of Discharge, including but not limited to laboratory parameters, will be conducted to discharge the subject from the clinic after 9 days in a confined setting. Use of CC will be allowed on Day 6, but only after spirometry has been performed.

- Safety follow-up period (from the time of Discharge on Day 6 to Day 13):

After time of Discharge, subject will enter a 7-day safety follow-up during which there will be recording of spontaneously reported new AEs/SAEs and the active follow-up of ongoing AEs/SAEs by the study site. In general, all AEs will be followed until resolved, stabilized (i.e., no worsening of the event), or a plausible explanation for the event has

been found. The end of the study is defined as the time of Discharge on Day 6 plus 7-day follow-up period.

During the study, any subjects who want to quit smoking will be encouraged to do so, and will be referred to medical services and will be withdrawn from the study. This is applicable for all subjects during screening to the baseline period and for subjects allocated to THS 2.2 or CC arms during the exposure period.

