7.5.1.2 Plasma Nicotine and Cotinine

Nicotine and cotinine concentrations will be measured in plasma to evaluate the exposure to nicotine. For subjects in the SA arm, blood samples will be collected on Days 0 to 4, at comparable time points. No nicotine PK profile will be done for subjects in the SA arm on Day 5 and Day 6.

- On Day 0 to Day 4 (all study arms):

One blood sample for nicotine and cotinine will be drawn each day between 08:00 PM-09:30 PM.

- Nicotine/cotinine PK Profile on Day 5 and Day 6 (THS 2.2 and CC arms only):

In total, 9 blood samples will be drawn on Day 5. The first blood sample on Day 5 will be drawn within 15 minutes prior to the first product use (=T0). On Day 5, T0 will serve as a

Confidentiality statement: Data and information contained in this document are considered to constitute trade secrets and confidential commercial information, and the legal protections provided to such trade secrets and confidential information are hereby claimed under the provisions of applicable law. No part of this document may be publicly disclosed without the written consent of Philip Morris Products S.A.

reference for the time to peak concentration. An additional 8 blood samples will be drawn in 2-hour intervals after T₀. The last blood sample should be drawn no later than 11:00 PM, corresponding to the end of the product use period. At all time-points, if the subject wants to smoke around the time of the blood draw, he/she should smoke first and the blood will be drawn after the product has been used. Depending on the time of the first product use, it may be that fewer than 8 blood samples will be collected from a subject after T₀.

On Day 6, two blood samples will be drawn. The first one will be 20 hours after T₀ and the second blood sample will be 24 hours after T₀ (with T₀ being the time of the first product use on Day 5).

- On Day 5 and Day 6 (SA arm only):

On Day 5, one blood sample will be drawn between 08:00 PM-09:30 PM.

On Day 6, one blood sample will be drawn between 08:00 AM-09:30 AM.

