9 STUDY ACTIVITIES

A detailed schedule of assessment can be found in Appendix 1. The time points shown are to be considered the time of assessment for the first subject. As not all subjects can be treated at the same time, a short time window will be implemented for subsequent subjects. Measurements not conducted at the exact time point, but conducted within the given time window (if applicable) do not constitute a protocol deviation but an accepted variability for the given time point.

In general, if no start time for the procedures is provided, then the procedure can be performed at any time during the day.

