9.2.4 Day of Discharge (Day 6)

Table 15 shows the assessments that will be performed on Day 6, prior to Discharge from the study unit:

Confidentiality statement: Data and information contained in this document are considered to constitute trade secrets and confidential commercial information, and the legal protections provided to such trade secrets and confidential information are hereby claimed under the provisions of applicable law. No part of this document may be publicly disclosed without the written consent of Philip Morris Products S.A.

Table 15. Time Schedule – Day 6

Time	Blood sample	Procedures	Additional information
		Day of Discharge procedures	
		AE/SAE recording; concomitant medication	All day until time of discharge
	√	Nicotine, cotinine in plasma	For THS 2.2 and CC arms: 20 hours and 24-hours blood sampling after T ₀ of Day 5. Each sample has a time window of +5 minutes For SA arm: between 08:00 AM-09:30 AM.
06:29 AM+/- 20min		Analysis sample to be taken after final portion of urine has been added to Day 5 sampling bottle	BoExp, creatinine, and Ames mutagenicity in 24-hour urine Risk markers: 8-epi-PGF2 α and 11-DTX-B2 Bio-banking for BoExp/ risk markers in 24-hour urine (if additional consent is obtained)
	√	CYP2A6 activity in plasma	To be done prior to smoking
		Assessment of cough (VAS)	To be done prior to smoking but not later than 10:00 AM
		MNWS questionnaire	To be done prior to smoking but not later than 10:00 AM
		Spirometry without short-acting bronchodilator	To be done prior to smoking
	√	Clinical laboratory parameters (hematology, clinical chemistry)	To be done after at least 10 hours of fasting
	√	Bio-banking for transcriptomics (if consent is obtained)	To be done after at least 10 hours of fasting.
	√	Bio-banking for BoExp/ risk markers in serum/plasma (if consent is obtained)	To be done after at least 10 hours of fasting
Before discharge		Urine safety analysis	
Before discharge		Urine pregnancy test (females only)	
Before 10:00 AM		Breakfast	

Confidentiality statement: Data and information contained in this document are considered to constitute trade secrets and confidential commercial information, and the legal protections provided to such trade secrets and confidential information are hereby claimed under the provisions of applicable law. No part of this document may be publicly disclosed without the written consent of Philip Morris Products S.A.

Before discharge	CO breath test	

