- e: Subjects will be asked if they plan to quit smoking within the next 3 months (at Screening only) and, in order to satisfy the protocol inclusion criteria, if they are ready to abstain from smoking for at least 5 days (at Screening and Day -2).
- f: THS 2.2 product test to be conducted as the last procedure of eligibility check at Day -2 (and after urine pregnancy test has been done in female subjects to exclude pregnancy).
- g: CO breath test; Days -1 to Day 5: the test will be conducted four times per day. The first test should be conducted within 15 minutes prior to the first product use (for subjects in the THS 2.2 and CC arms) and between 08:00 AM and 09:30 AM for subjects in the SA arm. The other three tests should be conducted between 12:00 PM and 01:30 PM, 04:00 PM and 05:30 PM, and 08:00 PM and 9:30 PM. Day -2 and Day 6: once during the visit, irrespective of the time of product use.
- h: COHb; Assessments should be done in conjunction with CO breath tests, where applicable. Day -1 to Day 4: one blood sample in the evening between 08:00 PM and 09:30 PM.
- Day 5: one blood sample within 15 minutes prior to the first product use (for subjects in the THS 2.2 and CC arms) and between 08:00 AM and 9:30 AM for subjects in the SA arm, and one blood sample between 12:00 PM and 01:30 PM, 04:00 PM and 05:30 PM, and 08:00 PM and 9:30 PM.

i: Nicotine/cotinine; Day 0 to Day 4 (all study arms): one blood sample in the evening between 08:00 PM and 09:30 PM.

Day 5 and Day 6 (THS 2.2 and CC arms): one sample within 15 minutes prior to the first product use (T0); eight blood samples after T0 each at 2 hour intervals. On Day 6, two blood samples will be drawn. The first sample will be 20 hours after T0 and the second blood sample will be 24 hours after T0 (with T0 being the time of the first product use on Day 5).

Day 5 and Day 6 (SA arm): on Day 5, one blood sample in the evening between 08:00 PM and 09:30 PM. On Day 6, one blood sample to be drawn in the morning between 08:00 AM and 9:30 AM.

j: QSU-brief: Daily, from Day -1 to Day 5.

k: MNWS: daily from Day 0 to Day 6.

l: MCEQ: Day -1 to Day 5 on a daily basis. On Day -1 and Day 0, all subjects will complete the questionnaire. From, Day 1, only subjects who are randomized to the THS 2.2 and CC arms will complete this questionnaire.

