7.2 Pharmacokinetic Parameters

The peak nicotine and cotinine plasma concentration (C_{peak}) and time to peak concentration (t_{peak}) will be obtained directly from the concentrations taken on Day 5. The weighted average concentration over 24 hours on Day 5 (C_{avg}) will be calculated by dividing the area under the curve from 0 to 24 h ($AUC_{0-24\text{ h}}$) by 24, where the $AUC_{0-24\text{ h}}$ is calculated using the linear trapezoidal rule.

Since the samples are taken whilst the subjects are smoking freely all samples must be non-missing for the parameters to be calculated as C_{peak} (and t_{peak}) could occur at any time.

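### Nothing requires the 24-hour nicotine/cotinine sample to precede the cigarettes allowed on Day 6, so Cavg in a THS 2.2 subject can include nicotine from a CC

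*Protocol*

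**What the plan says.** - **Day 6 smoking.** Protocol 6.6.1: "Smoking is also not allowed from Day 5, 11:00 PM until the spirometry has been performed on Day 6". Protocol 4.1: "Use of CC will be allowed on Day 6, but only after spirometry has been performed"; the Synopsis and SAP 6.1 repeat this. None of these limits the permission by arm. The ban on CC in the THS 2.2 and SA arms (6.6.1) ends on Day 5 at 11:00 PM.
- **Day 6 blood samples, THS 2.2 and CC arms.** Protocol Appendix 1: "The first sample will be 20 hours after T0 and the second blood sample will be 24 hours after T0". Table 15 (Protocol 9.2.4) lists the same draws, "20 hours and 24-hours blood sampling after" T0, with a window of 5 minutes.
- **Order of procedures on Day 6.** Table 15 requires the CYP2A6 sample, cough assessment, MNWS and spirometry to come before smoking. The nicotine/cotinine row has no such condition. Spirometry has no clock time, and Protocol 9 says "if no start time for the procedures is provided, then the procedure can be performed at any time during the day".
- **Smoking around a draw.** Protocol 7.5.1.2 says of a subject who wants to smoke near a draw: "he/she should smoke first and the blood will be drawn after the product has been used". Protocol 6.6.1 gives scheduled procedures priority over the wish to smoke and makes Day 5 the exception.
- **Use of the value.** Under SAP 7.2, Cavg "will be calculated by dividing the area under the curve from 0 to 24 h", by 24, with the linear trapezoidal rule and only if no sample is missing. SAP 12.6.2.3 compares Cavg between THS 2.2 and CC.

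**The concern.** Cavg is meant to describe nicotine and cotinine over the 24 hours that start with first product use on Day 5. Its last point is drawn on Day 6, after the exposure period has closed. By then the only stated condition for smoking is completed spirometry.

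The two Day 6 schedules are not linked. If spirometry ends before T0 + 24 h, a subject may be handed a cigarette while the draw is still to come. Tobacco Sticks are provided only from Day 1 to Day 5 (Protocol 6.5.1), and CC is the only product named for Day 6. In the THS 2.2 arm that cigarette is therefore the comparator product. In the CC arm it is the assigned product, used outside the exposure period. What is at stake is a clean THS 2.2 versus CC comparison of Cavg.

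**Working it through.** The plan gives no figure of its own on this point, so there is nothing to reproduce.

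**1. Does any rule close the gap?** The ban ends with spirometry, and spirometry is untimed. The 24 h draw is tied to T0 and has no pre-smoking condition. The priority rule in 6.6.1 settles the order when a draw is due and the subject wants to smoke. It does not cover a cigarette requested after spirometry and before the draw falls due. SAP 11 names use of a non-assigned product during the exposure period as a deviation, and that period ends on Day 5 at 11:00 PM. Day 6 CC use is expressly permitted. No rule clearly excludes it.

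**2. Weight of the 24 h value.** Sampling times are 0, 2, ..., 16, 20 and 24 h. Under the linear trapezoidal rule the last point enters AUC0-24 with half the last interval:

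(24 − 20)/2 = 2 h; weight in Cavg = 2/24 = 1/12 = 8.3%.

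The result is the same with 8, 7, 6 or 5 post-T0 samples on Day 5, because the last interval is always 20 to 24 h.

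**3. Effect in one subject.** Let D be the excess at 24 h due to Day 6 smoking. Cavg rises by D/12. The documents give neither D nor Cavg, so both are assumptions here:

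| Assumed D (ng/mL) | Rise in Cavg (ng/mL) | % if Cavg = 5 | % if Cavg = 10 | % if Cavg = 15 |
|---|---|---|---|---|
| 5 | 5/12 = 0.42 | 8.3 | 4.2 | 2.8 |
| 10 | 10/12 = 0.83 | 16.7 | 8.3 | 5.6 |
| 20 | 20/12 = 1.67 | 33.3 | 16.7 | 11.1 |

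**4. Effect on an arm mean.** If a share p of the arm is affected, the mean rises by p × D/12. With D = 10 and assumed p of 10%, 25% and 50%, that is 0.08, 0.21 and 0.42 ng/mL. The shift in THS 2.2 minus CC is this amount less the corresponding amount in the CC arm.

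**5. Length of the open interval.** Smoking hours in confinement start at 06:30 AM (6.6.1). The 24 h draw falls at the clock time of T0. The last Day 5 sample must be drawn by 11:00 PM (7.5.1.2), so k post-T0 samples at 2-hour spacing need T0 no later than 23:00 − 2k hours:

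- k = 8: T0 by 07:00 AM, interval at most 30 min
- k = 7: T0 by 09:00 AM, at most 150 min
- k = 6: T0 by 11:00 AM, at most 270 min

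Each can be 5 min longer because of the draw window. Any time spirometry takes after 06:30 AM shortens it. With T0 at 06:30 AM, or spirometry after the draw, there is essentially no gap.

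**6. Other values.** The 20 h sample falls before 06:30 AM for any T0 before 10:30 AM, so it is normally clear. Cpeak and tpeak come from Day 5 concentrations (SAP 7.2). The SA arm's Day 6 sample (08:00 to 09:30 AM) has the same gap, but no Cavg is derived in that arm.

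**The case against.** The strongest reply is that 6.6.1 already deals with this: scheduled procedures come before smoking, and the reverse order is an exception for Day 5. Much of that stands. A reader might infer from the heading of the profile in 7.5.1.2, which names both days, and from its wording about all time points, that a site is told to let subjects smoke before the Day 6 draw. The documents do not support that reading. The sentence sits in the Day 5 paragraph, before the separate Day 6 paragraph, and 6.6.1 confines the exception to Day 5. The gap that remains is narrower: a cigarette given between spirometry and a draw not yet due.

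The interval may also be short. If SAP 7.2 requires all eight post-T0 samples, every subject with a Cavg had T0 by about 07:00 AM. Cigarettes are handed out one at a time, and several procedures must come before the first. This is fair. However, 7.5.1.2 expects some subjects to have fewer than eight post-T0 samples, and the SAP does not say whether samples not taken because of a late T0 count as missing.

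A reader might also take the percentages above as an estimate of bias. They are not one: concentrations, rise and share affected are all assumed, the largest figure pairs the lowest Cavg with the highest D, and smoking in the CC arm may cancel part of any shift.

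The Day 6 bio-banking samples carry only a fasting condition, but the SAP plans no analysis of them, so they add nothing here.

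**Conclusion.** The point holds in a limited form. Followed as written, the plan lets a THS 2.2 subject smoke a CC after spirometry and before the T0 + 24 h sample, and that value enters Cavg with weight 1/12. The firm result is D/12 per affected subject; D and the number of subjects affected cannot be had from the documents. The interval is about 30 to 35 minutes at most if all eight post-T0 samples are required. It reaches about 150 minutes with seven, and more with fewer, if later starters are kept.

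Only Cavg is affected, one parameter under a descriptive secondary objective. Cpeak, tpeak, the primary endpoints, the success criterion and the sample size are not. It merits correction because the bias is avoidable and the correction costs almost nothing.

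**What to change.** **Protocol.** Reconcile the Day 6 smoking rule with the sampling schedule. In Table 15 and 7.5.1.2, attach to the 24 h nicotine/cotinine sample, and to the SA arm's Day 6 nicotine sample, the prior-to-smoking condition that Table 15 already uses for CYP2A6 and spirometry. The 20 h draw is then covered, since it comes earlier. Bring 4.1, 6.6.1 and SAP 6.1 into line so that they do not contradict the new condition. Word 7.5.1.2 to agree with 6.6.1, so that smoking before a draw clearly applies to Day 5 only.

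**SAP 7.2.** Flag any 24 h value drawn after logged Day 6 product use, report the count by arm, and repeat the Cavg analysis without those subjects as a sensitivity analysis. Do not set the value to missing: under the all-samples rule that could also remove Cpeak and tpeak, which are unaffected. State whether Day 5 samples not taken because of a late T0 count as missing.

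**Data needed.** Protocol 6.5.1 has dispensing times logged on each confinement day. Appendix 1 schedules butt collection only to Day 5, so confirm that Day 6 dispensing is logged.

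**Cost.** Wording only, with no extra sample or visit. Some late starters, and SA subjects who want to smoke, wait for their draw. If sampling is already complete, only the SAP part can be applied.

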6.6.2 Dietary Restrictions

A standard diet will be designed by a dietician for the whole confinement period. For each meal, the caloric and fat content should be controlled in order to avoid “high-fat” diet. The FDA guidance on food-effect studies for bioequivalency testing identifies a “high-fat” diet as a diet which maintains approximately 50 percent of total caloric content of the meal and is high in calories (approximately 800 to 1000 calories) (FDA, 2002).

In order to avoid any effect on assessment of BoExp, grilled or pan-fried meat, smoked pre-cooked meats (e.g. tuna, ham, corned beef, and meats), smoked bacon and sausage will not be permitted (Tiffany et al. 1991). In addition, to avoid any effect on the measurement of CYP1A2 activity, alcohol, broccoli, brussels sprouts, cauliflower, grapefruit and xanthine-containing foods and beverages (coffee, tea, chocolate, cocoa, mate, guarana etc.) will be forbidden (Faber and Fuhr, 2004) (except for the uptake of caffeine tablet for CYP1A2 measurement). Consumption of quinine-containing drinks (e.g. tonic water) is not allowed.

Subjects are not allowed to bring their own food or beverages to the investigational site. Meals will be served according to the schedules provided in Section 9. Additional light snack, fruits, and raw vegetables can be distributed to the subjects without restrictions at any time during confinement as long as they fulfill the above requirements described in this Section. Consumption of water is allowed as desired. The same menu and meal schedule will be administered uniformly for all subjects in all study arms. In addition, for the purpose of the Ames test planned on Day 0 and Day 5, the menus served on Day -1 and Day 4 will be identical. Fasting state has to be observed for at least 10 hours prior to blood draws for the safety laboratory at the Screening Visit, on Day 0, and Day 6, and for the serum/plasma bio-banking samples for BoExp/risk markers on Day 0 and Day 6 and blood bio-banking samples for transcriptomics on Day 0 and Day 6.

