7.5.2.4 Ames Mutagenicity Test

Urine mutagenicity, a biomarker for measuring mutagen load, will be measured on Day 0 and on Day 5 in 24-hour urine.

The urinary determination of each sample will be done in one bacterial strain (*S. typhimurium* strain YG1024), using S9 metabolic activation and 4 doses for each of the urine extracts.

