7.7.2 Urine samples

Spot urine samples will be used for the urine drug screen, urine cotinine screen, urine pregnancy tests, and safety urinalysis.

For the 24-hour urine collection, subjects will empty their bladders shortly before 06:30 AM on the study day indicated in the Schedule of Events (Appendix 1, Table A2). The collection period starts at 06:30 AM and ends on the following day at 06:29 AM. Shortly before 06:29 AM, after nearly 24-hours of urine collection, subjects will empty their bladder again and this urine will be used as the final portion of the 24-hour urine sample. During the sampling period, all urine passed must be collected and put into the sampling bottle, with the exception of about 10 ml for the spot urine tests (described above). No urine must be passed into the toilet. The start and the end time of the 24-hour urine collection will be recorded by the study site collaborator.

Confidentiality statement: Data and information contained in this document are considered to constitute trade secrets and confidential commercial information, and the legal protections provided to such trade secrets and confidential information are hereby claimed under the provisions of applicable law. No part of this document may be publicly disclosed without the written consent of Philip Morris Products S.A.

For assessment of urine BoExp, creatinine for normalization of urine BoExp, sample bio-banking and urine mutagenicity, aliquots from the 24-hour urine collection will be taken. In the Schedule of Events for the 24-hour urine collection (see Appendix 1, Table A2), the dot corresponds to the day on which the 24-hour urine collection period starts. For example, for NEQ measured at Day 5 in the 24-hour urine collection that starts on Day 5 and ends later on Day 6.

At time of Discharge on Day 6, subjects will empty their bladder shortly before 06:29 AM. This will be the last urine portion for the 24-hour urine for the Day 5 dot mark in the Schedule of Events.

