9.2.3 Exposure Period (Days 1 to 5)

The tables in this Section show the assessments that will be performed during the confinement period (Day 1 to Day 5). Table 10 shows the assessments that will be performed on Day 1:

Table 10. Time Schedule – Day 1

Time	Blood sample	Procedures	Additional information
Start of procedure		Day 1	
		AE/SAE recording; concomitant medication	All day
		Support during smoking abstinence (SA arm only) if needed	All day
Before 06:30 AM		Subjects are informed of their assigned study arm.	
6:29 AM+/-20min		Analysis sample to be taken after final portion of urine has been added to Day 0 sampling bottle. Must be prior to first product use of Day 1	BoExp, creatinine, and Ames mutagenicity in 24-hour urine Risk markers: 8-epi-PGF2 α and 11- DTX-B2 Bio-banking for BoExp/ risk markers in 24-hour urine (if additional consent is obtained)

Confidentiality statement: Data and information contained in this document are considered to constitute trade secrets and confidential commercial information, and the legal protections provided to such trade secrets and confidential information are hereby claimed under the provisions of applicable law. No part of this document may be publicly disclosed without the written consent of Philip Morris Products S.A.

Time	Blood sample	Procedures	Additional information
Start of procedure		Day 1	
6:30 AM+/-20min		Start collection to Day 1 sampling bottle	
		Assessment of cough (VAS)	To be done prior to product use but not later than 10:00 AM
		MNWS questionnaire	To be done prior to product use but not later than 10:00 AM
		CO breath test	Within 15 minutes before first product use (for THS 2.2 and CC arms) or between 08:00 AM-09:30 AM (SA arm)
06:30 AM-11:00 PM		HST	In THS 2.2 and CC arms, HST SODIM [®] device has to be used for all product uses if compatible CCs are smoked
6:30 AM		Beginning of product use	
Before 10:00 AM		Breakfast	
10:00 AM-11:30 AM		Vital signs (blood pressure, pulse rate, respiratory rate)	At least 5 minutes in supine position prior to measurement
12:00 PM-01:30 PM		CO breath test	
Before 02:30 PM		Lunch	
04:00 PM-05:30 PM		CO breath test	
Afternoon		Snacks	
In the evening until 09:00 PM		Dinner	
08:00 PM-09:30 PM		CO breath test	
08:00 PM-09:30 PM	√	COHb in blood	
08:00 PM-09:30 PM	√	Nicotine, cotinine in plasma	
08:00 PM - 11:00 PM		MCEQ questionnaire (THS 2.2 and CC arms only), QSU-brief questionnaire	

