12.6.3.7 Ames Mutagenicity Test

The 24 hour urine collection for the Ames mutagenicity test will be performed on Day 0 and Day 5.

Descriptive statistics of the values and change on Day 5 from Day 0 of the YG1024+S9 mutagenicity will be provided, along with listings.

The data will be presented in the below outputs, the TFL number refers to the TFL number in the accompanying TFL shell document:

TFL number	Title
TABLES	
15.2.4.47	Descriptive Statistics of Ames Mutagenicity Test (YG1024+S9) (units) – FAS
LISTINGS	
15.3.5.1	Listing of Mutagenicity Results and Changes from Baseline

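### The Ames menu-matching rule covers only the day before each urine collection, so the within-arm Day 0 to Day 5 change in mutagenicity is open to a diet effect

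*Protocol*

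**What the plan says.** Protocol 6.6.2 (Dietary Restrictions) requires that "the menus served on Day -1 and Day 4 will be identical". The same sentence gives both the reason for menu matching and the days it applies to: "for the purpose of the Ames test planned on Day 0 and Day 5, the menus served on Day -1 and Day 4". It sets no such rule for Day 0 and Day 5.

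Protocol 7.5.2.4 says that urine mutagenicity "will be measured on Day 0 and on Day 5 in 24-hour urine". SAP 12.6.3.7 agrees: "The 24 hour urine collection for the Ames mutagenicity test will be performed on Day 0 and Day 5".

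Protocol 7.7.2 fixes the clock times, "The collection period starts at 06:30 AM and ends on the following day at 06:29 AM", and the naming convention for the schedule in Table A2: "the dot corresponds to the day on which the 24-hour urine collection period starts". SAP 12.1.4 also names a collection by its first day.

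The planned output in SAP 12.6.3.7 is "Descriptive statistics of the values and change on Day 5 from Day 0", with listings and no model.

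Protocol 6.6.2 also provides that one menu and meal timetable applies to every subject in all three arms. It bans grilled, pan-fried and smoked meats, forbids subjects' own food, and leaves light snacks, fruit and raw vegetables unrestricted as long as they respect the bans.

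**The concern.** The menu sentence exists only because the sponsor judged that food could affect the Ames result. A control set up for that purpose would be expected to cover what is eaten while the urine is being collected. As written, it covers the preceding day and leaves the collection day free.

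If the Day 0 and Day 5 menus differ in a way that matters for urinary mutagenicity, each arm's Day 0 to Day 5 change contains that difference as well as any effect of the assigned product or of abstinence. A fall in the THS 2.2 or SA arm, read alone, could then be partly dietary. No planned model would separate the two.

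**Working it through.** The documents give no effect size, SD or power for the Ames test, so there is no stated figure to reproduce. The check is a calendar comparison.

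**Inputs**

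- Matched menus: Day -1 and Day 4 (Protocol 6.6.2).
- Collection window: 06:30 AM on the named day to 06:29 AM on the next day (Protocol 7.7.2).
- Ames collections: Day 0 and Day 5, named by start day (Protocol 7.5.2.4, 7.7.2 and Table A2; SAP 12.1.4 and 12.6.3.7).
- Aliquots: Table 10 takes the baseline Ames aliquot on the morning of Day 1 ("Analysis sample to be taken after final portion of urine has been added to Day 0 sampling bottle"). Table 15 takes the second on the morning of Day 6 from the Day 5 bottle.
- Meals: breakfast, lunch, afternoon snacks and dinner each day, with dinner over by 09:00 PM (Tables 8, 9, 13 and 14).

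**Step 1. Set the windows against the menu days.**

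| Ames collection | Opens | Closes | Scheduled meals inside | Matched menu day |
|---|---|---|---|---|
| Baseline | Day 0, 06:30 AM | Day 1, 06:29 AM | All of Day 0 | Day -1 |
| End of exposure | Day 5, 06:30 AM | Day 6, 06:29 AM | All of Day 5 | Day 4 |

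Scheduled meals that fall inside a collection window and come from a matched menu: 0 in either window.

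**Step 2. Gap between matched food and collection.** The last matched meal ends by 09:00 PM and the bottle opens at 06:30 AM: 3 h to midnight + 6.5 h = 9.5 h. This is an interval only. The documents give no excretion kinetics, so it does not show how much of the previous day's intake reaches the bottle.

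**Step 3. Where a menu difference would appear.** Let P be an arm's true Day 0 to Day 5 change due to its product or regimen, and d the shift caused by different menus on the two days.

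- Change within one arm = P + d. The shift stays in.
- Difference in change, THS 2.2 minus CC = (P_THS + d) − (P_CC + d) = P_THS − P_CC. The shift cancels if d is the same in both arms. The same holds against SA.
- Difference in Day 5 values between randomized arms: the Day 5 menu is common to all arms, so it cancels in the same way.

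If d varies with an arm's level of mutagenicity, the cancellation is partial. The documents contain nothing from which d, or its variation, could be estimated.

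**The case against.** The strongest reply is that the stated objective for this endpoint is a comparison between arms (Protocol 3.3 and 3.4.3). The menu is common to all arms, so a Day 0 versus Day 5 difference would largely drop out of the comparison, whether on Day 5 values or on changes. Summaries are presented by arm (Protocol 12.1.3), so a dietary shift would also show in the concurrent CC arm. This stands, and it confines the point to one arm's change read in isolation. A reader might infer that the THS 2.2 versus CC or SA comparison is biased; the documents do not support that.

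A second reply is that matching the preceding day may be deliberate, to limit carry-over into the collection. The same sentence names both pairs of days, which fits that reading. A reader might infer that the protocol simply mislabelled the days and that the rule serves no purpose as written. That is also unsupported: the documents state no carry-over rationale, but they do not exclude one. Carry-over is a reason to keep the Day -1 and Day 4 match; it does not explain leaving the collection days unmatched.

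Third, the diet is a dietician-designed standard diet with the main suspect meats banned on every day, which limits the likely size of any effect. This also stands.

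**Conclusion.** The point holds in a limited form. The rule in 6.6.2 controls the day before each Ames collection, and no passage requires the meals eaten during the two collections to match. The exposed quantity is the within-arm Day 0 to Day 5 change in SAP 12.6.3.7. The between-arm comparison is largely protected, on the assumption that a menu difference acts about equally in each arm.

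The size of any diet effect is unknown. It should not be assumed that the Day 0 and Day 5 menus in fact differ: the daily menus are not in the documents, which show only that a match is not required. The endpoint is exploratory and summarized descriptively, so no primary or secondary conclusion, power or error rate is affected. This is a cheap improvement rather than a defect that threatens the study.

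**What to change.** Amend Protocol 6.6.2 so that menus are identical on Day -1 and Day 4, and likewise on Day 0 and Day 5. This keeps any carry-over control and adds the missing match on the collection days.

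If the menus can no longer be changed, state in SAP 12.6.3.7 that the Ames change will be interpreted only by comparison with the concurrent CC and SA arms, and not as a within-arm effect. This may be the practical route, since SAP version 2.0 is dated 16 June 2014 and the protocol expected the study to end on 31 January 2014.

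The cost is one sentence and a small constraint on a menu plan that a dietician already prepares. No procedure or sample is added. The remedy is incomplete, because unrestricted snacks, fruit and raw vegetables mean that actual intake is still not fully matched.
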